3. PROTOCOL SYNOPSIS

Title:	Prospective, Multicenter, Single Arm Safety and Effectiveness Study of Endo Vascular Abdominal Aortic Aneurysm Repair Using the Nellix® System with Continued Access
Short Title:	EVAS I Study with Continued Access
Study Devices:	Nellix EndoVascular Aneurysm Sealing System (Nellix System)
Study Sponsor:	Endologix, Inc.
Objectives:	To study the safety and effectiveness of the Nellix System for Endovascular Abdominal Aortic Aneurysm (AAA) repair. Procedures will be performed per the instructions for use, and per institutional protocols and standard of care for endovascular aneurysm repair. As such, this study will evaluate the safety and effectiveness of the device system among a wide range of physicians and in consecutively enrolled subjects to assess outcomes generalizability.
Study Design:	Prospective, multicenter, single arm study with consecutive, eligible subject enrollment at each site. All subjects will undergo the Endovascular Aneurysm repair procedure with the Nellix System. Sites have been chosen with a suitable research infrastructure and physician experience in endovascular aneurysm repair to ensure adequate enrollment. Subjects will be followed procedurally to discharge, at 30 days (primary safety endpoint), six months, one year (primary effectiveness endpoint) and annually thereafter to five years (total follow-up commitment).
Investigators:	Physicians (vascular surgeons or interventional cardiologists/radiologists as part of a multi-specialty team with vascular surgeons) at sites in the United States, and the European Union with well-established experience in open repair and endovascular aneurysm repair techniques (i.e., ≥ 25 cases in the prior year) may participate. Details of the procedural and device usage techniques are incorporated into the study protocol on the basis of prior experience with an earlier generation device system, and more recent device refinements that have been developed. In those cases where the investigator is an interventionalist, a vascular surgeon must be immediately available during the procedure to perform any necessary surgical intervention.
Subject Population:	Patients diagnosed with an abdominal aortic or aortoiliac aneurysm who are considered candidates for endovascular repair and who meet the study eligibility criteria may be screened for enrollment in the study.
Enrollment:	Up to 180 subjects will be enrolled at a maximum of 30 sites in the EU, and US in the Primary Investigation. This max number includes up to 30 Roll-in subjects and up to 150 patients in the Intent to Treat Pivotal Cohort. In the Primary Investigation, a single site may not enroll more than 15% of the total enrollment. At enrollment closure for the Primary Investigation, an Extended Investigation will commence at these sites to enroll up to 250 additional subjects under continued access provisions,

with the same patient selection criteria and follow-up schedule and methods. Enrollment for this Extended Investigation cohort will occur during the Primary Investigation 1-year data collection. Enrollment closure of the Extended Investigation cohort will occur following completion of FDA review of the Pre-Market Approval (PMA) Application Submission.

Training: Initially, physicians will be directly supervised in each Nellix case by an Endologix trainer or Proctor. This training period will continue until a minimum of one case has been successfully completed and each investigator is cleared to proceed with Study enrollment without proctor supervision. This training requirement may be modified at the discretion of Endologix.

Inclusion Criteria:

1. Male or female at least 18 years old;
2. Informed consent understood and signed;
3. Patient agrees to all follow-up visits;
4. Have an infrarenal abdominal aortic aneurysm (AAA) with maximum sac diameter $\geq 5.0\text{cm}$, or $\geq 4.5\text{ cm}$ which has increased by $\geq 0.5\text{cm}$ within the last 6 months., or which exceeds 1.5 times the transverse dimension of an adjacent non-aneurysmal aortic segment.
5. Anatomic eligibility for the Nellix System *per the instructions for use*:
 - a. Adequate iliac/femoral access compatible with the required delivery systems (diameter $\geq 6\text{ mm}$);
 - b. Aneurysm blood lumen diameter $\leq 60\text{mm}$;
 - c. Proximal non-aneurysmal aortic neck: length $\geq 10\text{mm}$; diameter 18 to 28mm; angle $\leq 60^\circ$ to the aneurysm sac;
 - d. Most caudal renal artery to each hypogastric artery length $\geq 100\text{mm}$;
 - e. Common iliac artery lumen diameter between 9 and 35mm;
 - f. Distal iliac artery seal zone with length of $\geq 10\text{mm}$ and diameter range of 9 to 25mm;
 - g. Ability to preserve at least one hypogastric artery.
 - h. Ratio of maximum aortic aneurysm diameter to maximum aortic blood lumen diameter < 1.40

Exclusion Criteria:

1. Life expectancy < 2 years;
2. Psychiatric or other condition that may interfere with the study;
3. Participating in another clinical study
4. Known allergy to device any device component;
5. Coagulopathy or uncontrolled bleeding disorder;
6. Ruptured, leaking or mycotic aneurysm;
7. Serum creatinine level $> 2.0\text{mg/dL}$;

8. CVA or MI within three months of enrollment/treatment;
9. Aneurysmal disease of the descending thoracic aorta;
10. Clinically significant mural thrombus within the proximal landing zone (minimum 10mm) of the infrarenal non-aneurysmal neck (>5mm thickness over >50% circumference);
11. Connective tissue diseases (e.g., Marfan Syndrome)
12. Unsuitable vascular anatomy;
13. Pregnant (females of childbearing potential only).

**Primary
Endpoints:**

Safety: Major adverse events at 30 days.[†]

Effectiveness: Treatment Success at 1 year.

This is defined as procedural technical success and the absence of:

- Abdominal aortic aneurysm rupture;
- Conversion to open surgical repair;
- Endoleak Type I or Type III at 12 months
- Clinically significant migration[‡];
- Aneurysm enlargement; or
- Secondary endovascular procedure up to 12 months for resolution of:
 - Endoleak (Type I or Type III)
 - Device occlusion (may be due to thrombus or other causes)
 - Device migration
 - Abdominal aneurysm sac expansion
 - Device defect.[‡]

**Additional
Evaluations:**

Additional evaluations include:

- Procedural and in-hospital evaluations:
 - Anesthesia time;
 - Fluoroscopy time;
 - Contrast volume used;
 - Total procedure time;
 - Estimated blood loss;

[†]Defined as all-cause death, bowel ischemia; myocardial infarction, paraplegia, renal failure, respiratory failure, stroke, and procedural blood loss >1,000cc. Refer to protocol [§8.8.1](#) for detailed definitions.

[‡]Refer to protocol [§8.8.1](#) for detailed definitions.

- Incidence of transfusion;
- Time in ICU;
- Time to hospital discharge.
- Mortality (all-cause and aneurysm-related) within 30 days, at 6 months, and annually to 5 years;
- MAE Individual Components within 30 days, at 6 months, and annually to 5 years
- Composite Major Adverse Events at 30 days, 6 months, and annually to 5 years;
- Aneurysm rupture within 30 days, at 6 months, and annually to 5 years;
- Conversion to open repair within 30 days, at 6 months, and annually to 5 years;
- Adverse Events: All serious and non-serious events within 30 days, at 6 months, and annually to 5 years;
- Device performance (aneurysm sac diameter change from the first post-operative CT scan; device migration; incidence of endoleak) at 30 days, 6 months, and annually to 5 years;
- Renal function as assessed by estimated glomerular filtration rate (eGFR) pre-discharge and at 30 days, 6 months, and annually to 5 years;
- Device Patency and Integrity at 30 days, 6 months, and annually to 5 years;
- Luminal Thrombus Requiring Intervention at 30 days, 6 months, and annually to 5 years
- Secondary endovascular procedure or open surgery within 30 days, at 6 months, and annually to 5 years for resolution of endoleak (Type I or III), device occlusion, migration, aneurysm sac expansion and/or a device defect.

Schedule of Tests: Pre-procedural high resolution, contrast-enhanced CT scan evaluation to determine anatomical eligibility for enrollment will be performed within three months of the study procedure. Following EC/IRB approval of the study and the written informed consent form, patients will be screened for eligibility. Following informed consent, a physical exam and laboratory testing will be performed prior to the procedure. Subjects will be followed procedurally and to hospital discharge, and will then be followed at intervals: 30 days; 6 months; 1 year; and annually to 5 years.

Statistical Considerations:

Study Population: The Intent To Treat (ITT) population in this study consists of all subjects who are enrolled with an attempt to implant the Study Device. All roll-in subjects will be evaluated as a separate group. The subject is considered enrolled when the study device enters the access vessel.

The Per Protocol (PP) population in this study consists of all ITT subjects that have a device implanted and are alive when exiting the procedural room.

The Completed Cases (CC) population consists of all PP subjects that have completed 12 month follow-up visit.

Study Success, Safety: The primary safety analysis is **Major Adverse Events (MAE)**, as previously defined. The primary endpoint is to show that the percentage of subjects with an MAE is statistically superior to that in the Society for Vascular Surgery (SVS) open surgical control group at 30 days (56%). The hypothesis test

will be evaluated by the exact test as a one-tailed test, using significance level $\alpha=0.025$. Multivariable analyses will be used to assess predictors of success.

Study Success, Effectiveness: The primary effectiveness analysis is **Treatment Success**, as previously defined. The primary endpoint is to show that the proportion of subjects with Treatment Success is statistically superior to the target rate of 80% at one year. The hypothesis test will be evaluated using the exact binomial distribution as a one-tailed test, using significance level $\alpha=0.05$. Multivariable analyses will be used to assess predictors of success.

Additional Evaluations: Appropriate statistical methodology will be used to analyze all additional evaluations.

4. TRIAL OVERVIEW

4.1. OBJECTIVE

The objective of this study is to assess the safety and effectiveness of the Endologix Nellix® EndoVascular Aneurysm Sealing System for the endovascular repair of infrarenal abdominal aortic aneurysms (AAA). Procedures will be performed per the Nellix Instructions For Use (IFU) and per institutional protocols and standard of care for endovascular aneurysm repair. As such, this study will evaluate the safety and effectiveness of this device system among a wide range of physicians and in consecutively enrolled subjects to assess outcomes generalizability.

The principal risks related to aneurysms are rupture and thrombus migration. Aneurysms slowly and continually increase in size leading to the aneurysm rupture. The larger an aneurysm becomes, the likelihood of eventual rupture increases. The natural history of aortic aneurysms is to enlarge and rupture. Other potential complications of the aneurysm include compression of adjacent organs which may result in aortoenteric fistula, or aortocaval fistula. If the thrombus embolizes and flows down the blood stream, this can induce acute or chronic arterial obliteration of the lower limbs.

The risk of rupture is weighed against the risk of perioperative morbidity. The United Kingdom Small Aneurysm trial (UKSAT) reported 103 aneurysm ruptures in 2,257 subjects over a period of seven years, with an annual rupture rate of 2.2%.† The decision to treat a patient that presents with an asymptomatic aneurysm is primarily dependent upon the size of the aneurysm. Current Society for Vascular Surgery (SVS) practice guidelines recommend surveillance for most subjects with a fusiform AAA in the range of 4.0 to 5.4cm in maximum diameter; therefore, surgical repair of abdominal aneurysms of 5.5 cm or greater in diameter is recommended in healthy subjects, as is repair of saccular aneurysms. There are a number of qualifiers within the SVS guidelines that recommend AAA repair at 5.0cm, such as rapidly expanding aneurysms, and women.

It is estimated that approximately 25% to 40% of infrarenal AAA are not suitable for endovascular aneurysm repair (EVAR) due to unfavorable proximal neck anatomy (e.g., highly angulated, dilated, short, or encroaching on or involving the renal arteries).‡§ In most studies of endovascular AAA repair, the infrarenal non-aneurysmal neck length and angulation to the aneurysm sac requirements are ≥ 15 mm and $\leq 60^\circ$, respectively; shorter lengths or greater angulation have been reported to increase the risk of migration and type 1A endoleak and associated need for intervention.**††

The Nellix System was designed to withstand the migration and lateral displacement forces acting on endografts, while at the same time excluding the aneurysm sac lumen and minimizing endoleaks of any kind. The system is comprised of two independent flow channels, one to each iliac artery. Each flow channel consists of a balloon-expanded ePTFE covered stent surrounded by a Polymer-filled EndoBag which fills the blood lumen within the aorta, thus providing positional stability of the endograft and sealing the aneurysm completely from side-branch flow.[§] A clinical trial has been performed to assess the safety and effectiveness of the first generation Nellix system for endovascular AAA repair and results serve as the basis for CE Mark approval (October 2012); initial results to one year have been reported.^{**} Results of this trial demonstrate the versatility of the Nellix System in treating a variety of AAA anatomies, including those that have common iliac artery involvement bilaterally.

Continued clinical evaluation of the Nellix System in a broader group of institutions and physicians is therefore appropriate to assess the safety and effectiveness of the device for AAA repair and the generalizability of the approach.

4.3. STUDY DESIGN

This is a multicenter, prospective, single arm clinical study. Subjects with infrarenal AAA who are suitable candidates for endovascular repair using the Nellix System, based on protocol Inclusion/Exclusion criteria, will be considered for enrollment.

After this protocol and the patient informed consent form are reviewed and approved by the local Ethics Committee/Institutional Review Board (EC/IRB), patients having infrarenal AAA will be offered participation in the study. This will be accomplished through the patient's reading of the informed consent form in the patient's native language and discussion of the study with the patient by the Principal Investigator (PI) and site personnel. Agreement to participate and to attend all follow-up visits

^{*}Stavropoulos SW and Charagundla SR. Imaging techniques for detection and management of endoleaks after endovascular aortic aneurysm repair. *Radiology* 2007; 243(3):641-55.

will be documented with the patient's signature on the informed consent form, with appropriate signatures of the site PI and an impartial witness.

After providing written informed consent, screening and eligibility determinations will be performed by the site, Core Lab, Independent Anatomical Evaluation and Endologix. Subjects will undergo a high resolution, contrast-enhanced computed tomography angiography (CT) scan of the relevant aortic and aortoiliac vasculature within three months of the scheduled procedure. Evaluation of the aortic and vascular anatomy suitability per this protocol, as depicted on the CT scan, will be performed by the site PI and by an independent core laboratory and will undergo independent medical evaluation. Other tests include a physical examination, review of medical history for exclusionary conditions, and selected blood laboratory analyses. Endologix will notify, in writing, each potential patients final eligibility status before a case may be scheduled.

Following discharge from the hospital, the first follow-up visit will be made at 30 days (± 2 weeks). A CT scan will be performed to assess aneurysm morphology and device integrity and patency, as well as the status of the implanted devices. Subsequent follow-up visits will be made at six months, one year, and annually to five years per institutional standard of care for subjects with endovascular stent grafts. Enhanced post-operative follow-up visits are discussed in protocol [§8.5.6](#). Continued subject follow-up beyond five years is outside of the scope of this study. Nonetheless, all subjects should be monitored and evaluated per the institutional standards of care for patients with an implanted endovascular stent graft.

5. STUDY POPULATION

5.1. PRIMARY INVESTIGATION

Up to 30 sites in the EU, Canada, and the United States will enroll up to 180 subjects including 30 Roll-in subjects and up to 150 patients in the Intention to Treat Pivotal Cohort for endpoint analysis. Total enrollment at a single site is restricted to 15% of the Pivotal Cohort. Following investigator training, each PI will commence patient screening and enrollment under approval per applicable national and local clinical trial requirements* and complete a minimum of one (1) successful Nellix case (Roll-in) in their training phase. This training period may be modified at the discretion of Endologix. Physicians will be directly supervised in each case by designated Endologix staff.

Pivotal Cohort: Up to 150 subjects will be enrolled at a maximum of 30 sites in the US and the EU. This includes the statistically justified sample size of 132 plus an allowance for deviations from assumptions.

Roll-In Cohort: One (1) roll-in subject may be enrolled per site, therefore a maximum of 30 enrolled in the study, to allow for Investigator(s) to receive additional training on the Nellix System. Any roll-in subjects will be screened, consented, treated and followed identically to the main study cohort. However, the roll-in cohort of this study will be evaluated separately.

* Commercially approved clinical trial requirements in the EU (CE Mark), IDE approval in the US, and ITA approval in CA

Confidential. This document and the information contained herein may not be reproduced, used or disclosed without written permission from Endologix, Inc.

5.2. EXTENDED INVESTIGATION

Sites that participated in the Primary Investigation will be invited to participate in an Extended Investigation after enrollment closure of the primary investigation. This Extended Investigation will permit study site continued access to the Nellix System through the Primary Investigation's completion of the primary safety and effectiveness endpoint, and FDA review of the premarket approval (PMA) Submission. It is estimated that this Extended Investigation (Continued Access) phase will enroll an additional 150 patients.

Continued Access Cohort: Up to 250 patients will be enrolled into the Extended Investigation based on an enrollment rate of 0.5 patients per site per month and an estimated 20 months from the close of enrollment in the Primary Investigation. Enrollment in Extended Investigation (continued access) phase will be limited to the 27 US sites only as the Nellix System is commercially available to the three participating European sites.

5.3. INCLUSION CRITERIA

A patient who meets ***all of the following criteria*** potentially ***may be included*** in the study:

1. Male or female at least 18 years old;
2. Informed consent form understood and signed and patient agrees to all follow-up visits;
3. Abdominal aortic aneurysm with sac diameter $\geq 5.0\text{cm}$, or $\geq 4.5\text{cm}$ which has increased by $\geq 0.5\text{cm}$ within the last 6 months, or which exceeds 1.5 times the transverse dimension of an adjacent non-aneurysmal aortic segment.
4. Anatomically eligible for the Nellix System (per Instructions For Use):
 - a. Adequate iliac/femoral access compatible with the required delivery systems (diameter $\geq 6\text{ mm}$);
 - b. Aneurysm blood lumen diameter $\leq 60\text{mm}$;
 - c. Proximal non-aneurysmal aortic neck:
 - i. length $\geq 10\text{mm}$;
 - ii. diameter 18 to 28mm;
 - iii. angle $\leq 60^\circ$ to the aneurysm sac;
 - d. Most caudal renal artery to each hypogastric artery length $\geq 100\text{mm}$;
 - e. Common iliac artery lumen diameter between 9 and 35mm;
 - f. Distal iliac artery seal zone with length of $\geq 10\text{mm}$ and diameter range of 9 to 25mm;
 - g. Ability to preserve at least one hypogastric artery.
 - h. Ratio of maximum aortic aneurysm diameter to maximum aortic blood lumen diameter <1.40

5.4. EXCLUSION CRITERIA

A patient who meets ***none of the following*** criteria potentially ***may be included*** in the study:

1. Life expectancy <2 years as judged by the Investigator;
2. Psychiatric or other condition that may interfere with the study;
3. Participating in another clinical study;
4. Known allergy or contraindication to any device material;
5. Coagulopathy or uncontrolled bleeding disorder;
6. Ruptured, leaking or mycotic aneurysm;
7. Serum creatinine (S-Cr) level >2.0 mg/dL;†
8. CVA or MI within three months of enrollment/treatment;
9. Aneurysmal disease of the descending thoracic aorta;
10. Clinically significant mural thrombus within the proximal landing zone (minimum 10mm) of the infrarenal non-aneurysmal neck (>5mm thickness over >50% circumference);
11. Connective tissue diseases (e.g., Marfan Syndrome);
12. Unsuitable vascular anatomy that may interfere with device introduction or deployment;
13. Pregnant (female of childbearing potential only).

6. RESPONSE MEASURES

6.1. PRIMARY SAFETY

The safety endpoint is defined as the incidence of Major Adverse Events (MAE) at 30 days, defined as the composite of the following. Event definitions are provided in §[8.8.7](#)

- *All-Cause Mortality;*
- *Bowel Ischemia;*
- *Myocardial Infarction;*
- *Paraplegia;*
- *Renal Failure;*
- *Respiratory Failure;*
- *Stroke;*
- *Procedural Blood Loss ≥1,000mL*

Refer to §10.6 for primary safety endpoint analysis details.

†This criterion does not apply to patients on dialysis prior to study screening/enrollment.

Confidential. This document and the information contained herein may not be reproduced, used or disclosed without written permission from Endologix, Inc.

6.2. PRIMARY EFFECTIVENESS

The primary effectiveness endpoint is defined as the rate of Treatment Success at one year. Treatment Success is a composite of outcomes clinically relevant to the endovascular repair of infrarenal AAA as follows. Event and related definitions are provided in [§8.8.7](#).

Treatment Success: Procedural technical success [¶] and absence of:

- Abdominal aortic aneurysm rupture;
- Conversion to open surgical repair;
- Endoleak Type I or III at 12 months;
- Clinically significant migration[‡];
- Aneurysm enlargement; or
- Secondary endovascular procedure up to 12 months for resolution of
 - Endoleak (Type I or Type III)
 - Device obstruction or occlusion
 - Device migration
 - Abdominal aneurysm sac expansion
 - Device defect[‡]

Refer to §10.7 for primary effectiveness endpoint analysis details.

[¶] Procedural technical success is deployment of the Nellix System in the planned location and without unintentional coverage of both internal iliac arteries or any visceral aortic branches and with the removal of the delivery system.

[‡]Refer to protocol [§8.8.1](#) for detailed definitions.

Confidential. This document and the information contained herein may not be reproduced, used or disclosed without written permission from Endologix, Inc.

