- *Clinically significant migration*: Core Lab reported stent distal movement >10mm from the original implant location relative to the center of the distal renal artery resulting in an intervention or in a serious complication.
- *Occlusion*: Intervention for stent occlusion or as reported by the Core Lab.
- *Secondary procedure*: any non-diagnostic intervention after the index procedure intended to correct or repair an endoleak, device occlusion, migration, aneurysm sac expansion and/or a device defect (including infection).

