10.7.2 Sample Size

The primary trial effectiveness variable is the Treatment Success rate at one year post-operatively. Treatment Success is a composite of clinically-relevant outcomes, including procedural technical success and freedom from: aneurysm rupture; conversion to open repair; Type I endoleak at 12 months; Type III endoleak at 12 months; clinically significant migration; aneurysm sac enlargement; or secondary endovascular procedure up to 12 months for resolution of Type I or III endoleak, device occlusion, migration, aneurysm sac expansion and/or a device defect.

The sample size is obtained by using the exact binomial distribution using PASS 2008. A sample size of 132 subjects at one year in the study population will have 80% power against a null performance goal of 80% if the proportion of Treatment Success is 88% or higher. It is estimated that the rate of Treatment Success will be greater than 88%.

It is anticipated that the drop-out rate of the trial will be 12% or less. Because the larger of the two sample sizes after adjustment for loss to withdrawal is the one for effectiveness, a minimum

of $132/0.88 = 150$ subjects will need to be recruited for this study. Thus to allow for deviations from assumptions, 150 subjects will need to be recruited for this study.

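### The primary effectiveness composite counts only endovascular secondary procedures while the plan's own definition covers any route, so some open, non-conversion re-interventions are not failure events as written

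*Combined protocol and SAP*

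**What the plan says.** The primary endpoint is stated three times, each time limited to endovascular procedures: in the synopsis, in 6.2 ("Secondary endovascular procedure up to 12 months for resolution of" the listed problems) and in 10.7.2 ("secondary endovascular procedure up to 12 months for resolution of Type I or III endoleak, device occlusion", followed by the remaining indications).

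Other parts of the plan use a wider scope:

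- Section 6.2 tells the reader where to look: "Event and related definitions are provided in" section 8.8.7. That section defines a secondary procedure as "any non-diagnostic intervention after the index procedure intended to correct or repair an endoleak, device occlusion, migration, aneurysm sac expansion and/or a device defect", with no limit on route.
- The synopsis list of additional evaluations has "Secondary endovascular procedure or open surgery within 30 days, at 6 months, and annually to 5 years", so it names open surgery alongside the endovascular category.
- Section 6.3 uses the unrestricted term for the same additional evaluation. Section 10.8 goes back to endovascular procedures only.

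The only component of Treatment Success that names open surgery is conversion. Section 8.8.7 confines that to open repair of the abdominal aortic aneurysm itself, at any time and for any reason.

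**The concern.** The same device problem can be scored differently according to how it was treated. An occluded limb reopened by catheter within 12 months is a failure. The same occlusion treated by open thrombectomy or bypass is neither an endovascular procedure nor an open repair of the aneurysm. Occlusion is not a failure component in its own right; it enters the composite only through the secondary-procedure item.

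The plan foresees surgery of this kind. The distal ischemia definition in 8.8.7 covers surgical as well as percutaneous treatment, and stent graft occlusion treated by any route, but distal ischemia is not part of Treatment Success.

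The narrow wording can only add successes, in a single-arm test against a fixed 80% goal. Near the decision boundary one subject changes the result.

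**Working it through.** **1. Which open re-interventions fall outside the composite?** Taking the components in 6.2 with the definitions in 8.8.7:

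| Reason for open, non-conversion surgery up to 12 months | Failure as written? |
|---|---|
| Device occlusion | No |
| Device defect | No |
| Type I/III endoleak, resolved before 12 months | No* |
| Type I/III endoleak still present at 12 months | Yes, by its own component |
| Migration over 10 mm leading to intervention | Yes; clinically significant migration counts an intervention by any route |
| Migration of 10 mm or less | No |
| Sac enlargement over 5 mm | Yes, by its own component |
| Sac expansion of 5 mm or less | No |
| Rupture | Yes, by its own component |

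*Unless the leak could not be resolved at the index procedure and was still present on the 30-day CT. Section 8.8.7 makes that a technical failure.

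A "No" row leaves the subject a success only if every other component is also absent. Open repair of the aneurysm is always a failure, through conversion. Type II endoleak is outside the composite by any route.

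**2. The plan's own sample size.** Inputs from 10.7.1 to 10.7.3: exact binomial, one-sided α = 0.05, p0 = 0.80, p1 = 0.88, 132 evaluable, 12% drop-out.

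The cut c is the smallest r with P(X ≥ r | n, 0.80) ≤ 0.05.

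- n = 132: c = 114, attained α = 0.0383, power at 0.88 = 76.7%.
- n = 135: c = 116, attained α = 0.0490, power = 81.1%. In a search from 110 upwards this is the first n to reach 80%.
- 132/0.88 = 150, as stated. At n = 150: c = 129, attained α = 0.0372, power = 81.3%.

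The stated 132 is therefore within three subjects of the exact answer. The shortfall in power at 132 is a separate matter and nothing below depends on it.

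**3. Sensitivity at the boundary.** 114/132 gives p = 0.0383 and 113/132 gives p = 0.0625. 129/150 gives p = 0.0372 and 128/150 gives p = 0.0590. One subject moved from success to failure loses significance in either case.

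**4. Illustration of size.** Let X be the number of successes on the broader definition, with true rate 0.80. If exactly k failures are counted as successes, the test is won when X + k ≥ c, so the chance of a false win is P(X ≥ c − k | n, 0.80). The values of k are assumed, since the documents give no frequency.

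| k | n = 132 (c = 114) | n = 150 (c = 129) |
|---|---|---|
| 0 | 3.8% | 3.7% |
| 1 | 6.3% | 5.9% |
| 2 | 9.7% | 8.9% |
| 3 | 14.2% | 12.9% |

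If k is instead an average, so that the success probability becomes 0.80 + k/n, the figures for k = 1, 2, 3 are 5.9%, 8.9% and 13.0% at n = 132, and 5.6%, 8.3% and 11.9% at n = 150. Under either model one such subject takes the error above the nominal 5%.

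**The case against.** Four replies deserve weight.

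- **Other components catch much of this.** They do, as the first table shows. A reader might infer that any open re-intervention short of conversion leaves the subject a success; the documents do not support that. Open ligation for a leak is also a weak example, because ligation of a collateral concerns a Type II leak, which would not count even under the wider wording.
- **An adjudicator might already apply the wide definition.** Section 8.8.7 has no entry for a secondary endovascular procedure, only the unrestricted term, and the Clinical Events Committee works from both the event definitions and the endpoint criteria (11.2). The plan also uses the word endovascular loosely elsewhere in 8.8. This makes the actual scoring uncertain, but it does not remove the conflict: three statements of the endpoint agree on the narrow scope.
- **The inflated error is relative to the broader endpoint.** Correct. Against the endpoint as written, the exact test stays below 5%. The 80% goal and the 88% planning rate are given in 10.7.2 alongside the narrow composite. If the restriction is deliberate, though, the plan gives no reason for it and points to a definition that contradicts it.
- **Changing the endpoint now would be a change after data were seen.** This stands. Section 8.6 describes a report to the FDA in October 2016 based on two-year follow-up, and Revision 11.6 is dated April 2018. It argues for reporting both readings, not for leaving the wording unreconciled.

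**Conclusion.** The inconsistency is established by the text and lies in the primary endpoint. The gap is limited to open, non-conversion surgery up to 12 months for device occlusion, device defect, a Type I/III endoleak resolved before 12 months, or migration or sac expansion below the composite's thresholds, in subjects with no other failure component. Its direction is certain: it can only raise the success count. Its size is unknown. The range of one to three subjects is an assumption, as are a true rate of exactly 80% on the broader endpoint and full evaluability at 132 or 150.

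A reader might go further and infer that the one-year result was in fact inflated. The documents do not show that any such procedure took place, or how one would have been adjudicated.

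**What to change.** In the synopsis, 6.2, 10.7.2 and 10.8, replace the endovascular term with *Secondary procedure (endovascular or open surgical, as defined in 8.8.7)*. Keep the existing list of indications. The list matters because the 8.8.7 definition does not restrict endoleak type, so without it Type II treatments would enter the composite.

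Because follow-up data preceded this version, the endpoint should not be replaced silently. The sponsor should:

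1. state which definition was applied to the one-year analysis;
2. count the open, non-conversion procedures by indication;
3. report Treatment Success under both readings against the 80% goal.

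No new data are needed: 8.8.4 already asks for the specific procedure to be identified on the Adverse Event eCRF. The cost is the wording, one extra analysis and a success rate that may be slightly lower. A small drop can matter for power. If 88% was meant for the narrow composite, a rate one percentage point lower takes exact power at n = 132 from 76.7% to 64.6%.
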